#### Sample Size Determination and Power Analysis

This is a pilot study with an aim towards developing estimates for effect sizes that can be used to design a larger, confirmatory randomized clinical trial. A sample size of 20 per group will allow us to detect a difference of 25% between groups for our primary outcome of the four square step test. We will enroll 40 subjects. Typical attrition rates are 25 to 30%, primarily due to time conflicts and development of non-study related medical problems. In our preliminary studies, MMBI decreased the time to complete the four square test by 24%, with even greater improvements in the frailest subjects. Time to complete the four-square test has been shown to be an excellent biomarker for fall risk.

For our second exploratory Aim the outcome will be the rate of falls and the proportion of fallers during the intervention. The sample size estimate is determined primarily by three factors; the baseline rate of falls in the study population, the duration of follow-up, and the differential impact of the two interventions on the fall rates. For example in the Lifestyle integrated Functional Exercise (LiFE) program, which embedded balance and lower limb strength training into habitual daily routines there was a statistically significant 31% reduction in fall rates (1.66 per person years) compared to controls (2.28 per person years), whereas the structured lower limb strength and balance exercises had a non-significant 19% reduction (1.90 per person years) in fall rate compared with the controls. Based on this and other literature we estimate that setting the power at 80%, alpha at 5% and with a drop-out rate of 20%, a sample size of 90 is required in each group to detect a clinically significant difference of 25% reduction in falls frequency between the two groups. Due to the budgetary limitations and duration of this VA SPIRE grant it is not feasible for us to enroll and study 180 subjects. Thus we recognize that we might not have sufficient power to see a difference in fall rate and number of falls between groups. Results from this study will be used to power a larger randomized clinical trial that will examine the effectiveness of the two interventions to reduce rate of falls and risk of falling in older veterans at high risk for falls.

Statistical Analysis: Data analyses will be performed using SAS. We will first perform an exploratory analysis to look for extreme values to make sure they are not the result of data entry error. All analyses will be conducted using the intention-to-treat principle. Statistical significance will be at an alpha of 0.05 (two-tailed). Demographic and clinical characteristics at baseline will be summarized with standard descriptive statistics.

For aim 1, to compare changes (defined as 24-week value minus baseline value) in mobility, balance and strength between our two groups (tai chi and MMBI) after 24 weeks of intervention we will use ANOVA for all continuous outcome measures (change=group).

For Aim 2 We will use Poisson regression (or, if the data are overdispersed Quasipoisson or negative binomial regression) to compare the number of falls in our two experimental groups. This methodology has been employed in the LiFe trial and other studies.

Project time line: Prior to the start of the funding, we will obtain regulatory approvals from the IRB and VA R&DC. We will recruit 3 sets of intervention cohorts. Recruitment and baseline testing of the first cohort will start at the start of the funding period and they will enter intervention at month 3. While this first cohort is undergoing intervention we will recruit and perform baseline testing on the second cohort who will enter the intervention approximately 6 months after the start of the study. Post intervention testing on the first cohort will commence at 9 months. Recruitment for the third cohort will be done while the second cohort is in intervention and the third cohort will start their intervention at 9 months. During months 21 to 24 we will perform data analysis, and start writing manuscripts. We have used a similar strategy of staggered cohorts in prior studies. The study will be completed in a two years.

Anticipated Results and Alternate Findings: While we do not anticipate that Tai Chi will result in larger improvements in balance and falls than MMBI it is possible. The strength, balance, and gait tests that we are performing allow us to evaluate the contribution each makes to improving balance. This information can be used to design a future larger study aimed at decreasing falls.

Barriers: 1) Recruitment is always a potential challenge in clinical investigation. We have a long history of enrolling veterans into intervention studies. We have established a patient recruitment core and subject registry. We will work with this core to recruit veterans into this study. Given the high prevalence of older veterans who experience falls, we do not anticipate difficulties in recruiting and enrolling the requisite number of veterans into this RCT. 2) Poor adherence is also a potential problem. In our pilot study 16 out of 17 individuals completed our MMBI protocol with > 90% adherence. The majority of the individuals enjoyed the group sessions and looked forward to attending. We anticipate that we will have similar adherence to this program.

Project management plan: [name] will meet on a weekly basis with the investigative team to discuss: review of newly screened and enrolled volunteers; study conduct, adverse events; quality of data, and monthly to discuss the status of subject testing and training (show rate, completion rate, exercise logs); review of rates of enrollment; new literature findings that may impact on the conduct of the study

Quality Assurance Plan: The BVAMC GRECC has well established quality management, quality assurance and safety monitoring plans that will be employed in the oversight of this study. The principal investigator is responsible for ensuring that all research conducted in this study follows good clinical practice guidelines and are carried out according to IRB regulations.

Future Directions: We have designed this study with community integration in mind. Both the Tai Chi and MMBI are easily exportable to a community program. Our MMBI program uses commonly available equipment for both balance training (chairs, cushions, step benches etc) and strength training (body weight, ankle weights, or commonly available gym equipment). We plan to use the results of this pilot project to write a multicenter QUERI grant or multisite Merit that focuses on community integration of these projects for fall prevention. We anticipate that the results of this project will support the development of an MMBI program in other VAs.

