### Preliminary Studies:

We have assembled a highly qualified team of investigators with extensive expertise in performing exercise rehabilitation studies in older veterans. Seventeen older ( $75.6 \pm 4.5$ ) adults with a history of falls were recruited for a preliminary study utilizing MMBI. Subjects performed the intervention in our exercise facility 3 times/week for 16 weeks and were instructed in a home regimen to continue after completion of the center-based portion of the intervention. 16 out of 17 individuals completed all portions of the study with > 90% adherence to the protocol. Six of the 16 fell at least once during the 4 month study, and an additional six subjects reported at least 1 near fall. Four-square step times (FSST) in those who fell were significantly slower ( $12.7 \pm 6.5$  seconds) than in those who did not fall ( $5.98 \pm 2.12$  seconds), ( $p=0.009$ ). Notably, however, these individuals also had the greatest improvement with the intervention. After 16 weeks of MMBI scores on the functional gait assessment (FGA) increased by 12% and the time to complete the FSST decreased by 24%. Individuals with FSST > 10 seconds at baseline made even greater improvements of 40-50% on the FSST and FGA. Furthermore these improvements were maintained for 4 months after the completion of the exercise program. These findings warrant the application of our MMBI program to a larger study of greater duration with an active comparison group, particularly in those with a FSST > 10 seconds at baseline.

Parameter (N=16)	Baseline (mean $\pm$ SD)	16 week Post-intervention(mean $\pm$ SD)	P value
BMI (kg/m  )	26.9 $\pm$ 3.2	27.0 $\pm$ 3.2	0.40
Four-square (sec)	8.5 $\pm$ 5.3	6.1 $\pm$ 2.7	0.04
Functional gait assessment*	22.7 $\pm$ 5.9	25.5 $\pm$ 5.2	0.01
Leg extension strength	278.80 $\pm$ 110.5	299.00 $\pm$ 114.9	0.05

\*N of 8, measurement only performed on second cohort

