### Methods/Study Procedures:

Approach: We will enroll 56 older community dwelling veterans (age > 65 years) with a fall in the past year and evidence of balance dysfunction (FSST > 10 seconds). Our preliminary findings suggest that those with higher FSST benefit the most from MMBI. After baseline testing, individuals will be randomized to either MMBI or to a Tai Chi intervention. All participants will participate in a group exercise class in their assigned intervention for 1 hour, 3 times per week for 24 weeks. To promote camaraderie and accountability among subjects they will be enrolled in intervention cohorts of 8 to 10 subjects. At randomization subjects will be stratified first by gender then by FSST. Assessments will occur at baseline and after completion of the intervention and will include balance, mobility and fall risk, lower extremity strength, and muscle composition (total body DXA scan, hip and thigh CT scan). All participants will be followed from initial enrollment until 6 months after completion of the post-intervention testing (6 months follow up) utilizing calendar diaries, post-cards and monthly phone calls from the study coordinator to determine the number of falls, near falls, injuries and fall related medical visits.

Recruitment and Screening: A variety of methods will be used to recruit older veterans with a history of a fall in the last year, including the Baltimore GRECC subject recruitment registry, advertisements, provider referrals, community outreach, outpatient clinics and the emergency department at the VAMHCS. The use of multiple recruitment strategies will allow us to maximize our outreach to a diversity of veterans including those who have yet to seek routine care at the VA. A fall will be defined as any event that resulted in a person coming to rest unintentionally on the ground or other lower level. Prospective studies have demonstrated that older adults with a history of falls are more likely to experience subsequent falls. Exclusion criteria will include: dementia, unstable angina, poorly controlled hypertension, active substance abuse, poorly controlled diabetes, progressive neurodegenerative disease, and any other major orthopedic or health condition that would limit ability to safely exercise (see human subjects section for more

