Aim 1: Primary Outcome Measures: Four-Square Step Test (FSST) and Functional Gait Assessment Tests (FGA). The primary outcome measures will be the change from baseline to 24 weeks in the FSST and the FGA. The FSST is a test of dynamic balance ability that assesses an individual's ability to change directions while stepping. Subjects will be timed as they step over four canes set-up in a cross on the floor. Participants will be closely guarded as they perform the test to prevent any falls. The FSST is an ideal outcome measure as it assesses the ability of an individual to dynamically maintain an upright posture while changing directions and weight shifting. It has excellent inter-rater reliability (ICC=0.99), test-retest reliability (ICC=.98), sensitivity (92%) and specificity (93%) in older adults. Older adults who take > 15 seconds to complete the task are at increased risk for multiple falls.

The FGA will also be used as a primary measure of dynamic mobility and balance and to assess fall risk. The FGA is a 10-item clinical gait test that is based on the dynamic gait index (DGI). It tests higher level dynamic gait activities that are part of daily functional mobility such as turning safely, walking at speeds required to safely cross a street, the ability to walk with head turns, gait with a narrow base of support and ambulating backwards. Each of the ten items is scored 0 to 3, with total scores ranging from 0 to 30. Scores below 22 are predictive of future falls. The FGA has excellent inter-rater reliability (ICC=.93) and predictive validity for falls. The FGA is an ideal outcome for this balance study in older veterans.

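### The 25% FSST detection claim assumes 20 per group, which 40 enrolled with 25-30% attrition does not leave, and its missing inputs mean it cannot be verified

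*Combined protocol and SAP*

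**What the plan says.** - Sample Size Determination and Power Analysis: "A sample size of 20 per group will allow us to detect a difference of 25% between groups for our primary outcome", the FSST. The next two sentences read "We will enroll 40 subjects" and "Typical attrition rates are 25 to 30" (per cent). The paragraph then cites a 24% fall in FSST time under MMBI in the preliminary study.
- The same section sets 80% power only for the exploratory falls aim, where it concedes that power may be too low. It makes no such concession for FSST.
- Methods/Study Procedures, Approach: "We will enroll 56 older community dwelling veterans", with "evidence of balance dysfunction (FSST > 10 seconds") as an entry condition.
- Statistical Analysis: two-tailed alpha of 0.05; for Aim 1, an ANOVA of change (24-week value minus baseline) with group as the only term.
- Preliminary Studies: the table row "Four-square (sec") gives 8.5 ± 5.3 s before and 6.1 ± 2.7 s after 16 weeks of MMBI, N=16, p=0.04. The text adds: "Four-square step times (FSST) in those who fell were significantly slower", with 12.7 ± 6.5 s in the six who fell.
- Aim 1: Primary Outcome Measures: "Older adults who take > 15 seconds to complete the task are at increased risk for multiple falls".

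**The concern.** This is the only sample-size statement for either primary outcome (FSST and the Functional Gait Assessment), and it is worded as a certainty. Two things undermine it. The number of analysable participants that it relies on does not follow from the enrolment and attrition given beside it. And none of the inputs needed to check the 25% is stated.

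What is at stake is how a non-significant FSST result is read. Someone who trusts the sentence would take such a result as evidence against a 25% difference. The documents do not establish that the trial could support that conclusion. The stated purpose is to estimate effect sizes for a larger trial, yet no expected precision is given.

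**Working it through.** **1. Evaluable numbers (no SD needed).** Inputs: 40 or 56 enrolled; 25-30% attrition; two arms, with 1:1 allocation implied by 20 per group of 40. Attrition is taken to mean no 24-week FSST value.
- 40 × 0.75 = 30, or 15 per arm; 40 × 0.70 = 28, or 14 per arm.
- 56 × 0.75 = 42, or 21 per arm; 56 × 0.70 = 39.2, or 19.6 per arm.

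So 20 evaluable per group fits 56 enrolled and does not fit 40.

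**2. Reproducing the plan's 20.** This cannot be done, because base, SD of change and power are not stated. Assuming 80% power and a normal approximation, an SD of 2.7 s with a 10 s base gives 19 per group, and an SD of 4.27 s with a 15 s base gives 21. Either would come close to 20, but the plan states neither.

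**3. The 24%.** It compares MMBI participants with their own baseline. The trial compares MMBI with Tai Chi, which the introduction also expects to improve balance. A within-group fall of 24% is therefore not evidence for a 25% difference between groups.

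**4. Illustration from the pilot table.** Assumptions: p=0.04 is from a paired t-test on N=16, and the 25% is of the baseline mean.
- Two-sided p=0.04 on 15 df gives t = 2.249.
- SD of change = (8.5 − 6.1) × √16 / 2.249 = 9.6 / 2.249 = 4.27 s.
- Implied r = (5.3² + 2.7² − 4.27²) / (2 × 5.3 × 2.7) = 0.60.

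Power of the planned test (noncentral t, two-sided 0.05, SD of change 4.27 s):

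| Baseline mean | 25% of it | 20 per arm | 14-15 per arm |
|---|---|---|---|
| 10 s (entry threshold) | 2.5 s | 44% | 32-34% |
| 12.7 s (pilot fallers) | 3.175 s | 63% | 47-50% |
| 15 s | 3.75 s | 77% | 61-64% |

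The 10 s row is a floor at this SD, since every participant must exceed 10 s.

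**5. Detectable difference and precision at SD 4.27 s.**
- 80% power, 20 per arm: 0.909 × 4.27 = 3.9 s. With 15 per arm: 1.060 × 4.27 = 4.5 s. With 14: 1.100 × 4.27 = 4.7 s.
- Half-width of the 95% CI for the group difference, t × SD × √(2/n): 2.024 × 4.27 × √(2/20) = 2.7 s with 20 per arm; 2.048 × 4.27 × √(2/15) = 3.2 s with 15; 2.056 × 4.27 × √(2/14) = 3.3 s with 14.

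**6. How firm the illustration is.**
- Sampling error: the 95% interval for an SD on 15 df (normality assumed) is about 3.15-6.61 s. That gives 32-87% power at 12.7 s with 20 per arm.
- Selection: apply the > 10 s criterion to the pilot means and SDs with r = 0.6. A normal model gives a mean of 13.7 s, an SD of change of 3.0 s and about 95% power with 20 per arm. A lognormal model gives 15.0 s, 5.0 s and about 63%. The normal model fits poorly, since it puts about 5% of times below zero.

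The documents do not settle which of these applies.

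**The case against.** The strongest reply is that the illustrative powers are not for the population to be enrolled. The 10 s figure is the edge of the eligible range. The 12.7 s figure is the mean of six pilot participants who fell and were not selected on FSST. The SD of change comes from a pilot group with a mean of 8.5 s. Selecting people above 10 s changes both the mean and the SD, and on some distributions power is well above 80%. All of this stands.

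A reader might therefore be tempted to infer from the table that the trial has 44% or 63% power, or that the claim is false or probably optimistic. The documents do not support that. They give no SD for people above 10 s and do not name the test behind p=0.04. They leave the base of the 25% open: the table means fall by 2.4/8.5 = 28% while the text reports 24%, so the sponsor may be working with individual percentage changes.

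It can also be said that 40 is meant as the number of completers. The 56 fits that. So do three sets of cohorts of 8-10, which come to 48-60 if each set has one cohort per arm. This is plausible, but the sample-size section says that 40 will be enrolled, and then gives an attrition rate without applying it. Intention-to-treat analysis does not restore the missing participants, since a change score needs a 24-week value and no handling of missing values is described.

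Lastly, this is a pilot, and no decision rule depends on FSST significance. That limits the harm. But the plan chose to make a detection claim, and qualified only the falls outcome.

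**Conclusion.** The point holds in two parts. First, the sample-size section's own enrolment and attrition figures leave 14-15 evaluable per arm, not the 20 on which its claim rests, and they conflict with the 56 in the Approach paragraph. This rests only on attrition meaning loss of the 24-week measurement. Second, the 25% detection claim cannot be verified, because base, SD of change and power are missing and the 24% offered in support is a different quantity.

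The power figures are an illustration of scale under the two assumptions stated in the working. At the pilot SD, a true 25% difference on a 12.7 s mean would be missed in about 37% of trials with 20 per arm and in 50-53% with 14-15. Actual power could be above or below 80%, so the claim is unverified, not shown to be wrong. The missing inputs alone would be a reporting gap. The unmet 20 per group makes the point worth correcting.

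**What to change.** 1. Reconcile 40 with 56 enrolled, and state that 20 per group means evaluable at 24 weeks.
2. Replace the unqualified sentence with the difference detectable at 80% power, two-sided 5%, under the planned ANOVA of change for the evaluable number. Name the base and the SD of change, and show a range because the SD above 10 s is unknown. On the pilot SD the figures are about 3.9 s with 20 per group and 4.5-4.7 s with 14-15.
3. Add the expected 95% CI half-width, since estimation is the stated aim: about 2.7 s with 20 per group and 3.2-3.3 s with 14-15, on the same SD.
4. Extend the low-power caveat to FSST, unless the sponsor has inputs that support the 25%; if so, state them.

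The cost is a reworded paragraph and a less favourable stated figure. The restatement itself needs no extra patients.

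### The plan gives two enrolment targets, 56 and 40; enrolling 40 with the stated 25–30% attrition leaves 14–15 evaluable per group, not the 20 per group in the power statement.

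*Combined protocol and SAP*

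**What the plan says.** Methods/Study Procedures (Approach): "We will enroll 56 older community dwelling veterans (age > 65 years) with a fall in the past year". The same paragraph adds that FSST must exceed 10 seconds, and says of the exercise classes that "they will be enrolled in intervention cohorts of 8 to 10 subjects".

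Sample Size Determination and Power Analysis: "A sample size of 20 per group will allow us to detect a difference of 25% between groups" on the FSST, then "We will enroll 40 subjects. Typical attrition rates are 25 to 30" per cent. No power, standard deviation or base for the 25% is given for the FSST.

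For the exploratory falls aim, the same section uses a different loss figure: "setting the power at 80%, alpha at 5% and with a drop-out rate of 20" per cent.

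Project time line: "We will recruit 3 sets of intervention cohorts".

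The Aim 1 outcome and analysis text defines the primary outcomes as change from baseline to 24 weeks. The Statistical Analysis section names intention-to-treat and two-sided testing at 0.05, and gives no method for missing 24-week values.

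**The concern.** Both statements use the verb enrol, for the same trial, and they differ by 16 people. Nothing in the document says that one number counts participants entered and the other counts completers.

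The sample-size paragraph also conflicts with itself. Forty enrolled is exactly two groups of 20, so the number enrolled equals the number the power statement needs, yet the next sentence expects a quarter or more to be lost. As a participant without a 24-week test has no change score, those losses come straight out of the primary comparison.

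Two things are at stake. The trial has no single enrolment target to be held to, and a team working from the sample-size section could properly stop at 40. If it does, the FSST comparison rests on about 30 people, and the effect-size estimates that the pilot is meant to supply are less precise than planned.

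**Working it through.** **Inputs from the documents.** Enrolment 56 (Methods) or 40 (sample-size section); 20 per group for the FSST claim; attrition 25–30%; two-sided alpha 0.05 (Statistical Analysis).

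**Assumptions.** Equal allocation, inferred from 20 per group and 40 in total. For power only, 80% at 20 per group, with 70% and 90% as alternatives, because the plan gives no power for the FSST.

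**1. The plan's own figure.** The 20 per group cannot be reproduced, because the SD, the power and the base of the 25% are missing. Using the pilot results as stand-ins (bases of 8.5, 10 and 12.7 s; SDs from 2.7 to 6.5 s; 80% power; normal approximation), the required number runs from 12 to 147 per group. One pairing, base 10 s with SD 2.7 s, gives 19. The 20 is therefore taken as stated.

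**2. Evaluable numbers.** Evaluable = enrolled × (1 − attrition).

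| Enrolled | Attrition | Evaluable | Per group |
|---|---|---|---|
| 40 | 25% | 40 × 0.75 = 30 | 15 |
| 40 | 30% | 40 × 0.70 = 28 | 14 |
| 56 | 25% | 56 × 0.75 = 42 | 21 |
| 56 | 30% | 56 × 0.70 = 39.2 | 19.6 |

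**3. Enrolment needed to keep 20 per group.** 20 / 0.75 = 26.7, so 27 per group (54 in total). 20 / 0.70 = 28.6, so 29 per group (58 in total). The 56 lies between these. Going from 56 to 40 implies attrition of 1 − 40/56 = 28.6%, inside the stated range.

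**4. Effect on the detectable difference.** Two-sample t-test, two-sided 0.05. At 80% power the detectable standardised difference is 0.909 at 20 per group, 1.060 at 15 and 1.100 at 14. Scaling the plan's 25%:

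- 15 per group: 25% × 1.060 / 0.909 = 29.1%
- 14 per group: 25% × 1.100 / 0.909 = 30.3%

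The ratio hardly depends on the assumed power: 70% and 90% also give about 29% and 30%.

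**5. Effect on power for the 25% difference.** This does depend on the assumption.

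| Power assumed at 20 per group | At 15 per group | At 14 per group |
|---|---|---|
| 70% | 57% | 54% |
| 80% | 67% | 64% |
| 90% | 79% | 76% |

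**6. Cross-check on class sizes.** If each of the three sets has one class per arm, the total is 3 × 2 × (8 to 10) = 48 to 60, which contains 56 but not 40. One class per arm is an inference from the separate MMBI and Tai Chi sessions described in Methods. The time line also speaks of each cohort in the singular; three classes in all would give 24 to 30, which matches neither target.

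**The case against.** **The 40 was probably meant as completers.** The arithmetic makes this likely, but the text says enrol, and nothing in the section mentions 56.

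**Screening failures could link the two numbers.** Methods expects 20–30% of those brought in for screening not to qualify, and consent comes before screening. If 56 counted people consented, 56 × 0.70 to 0.80 = 39 to 45 would go forward, again about 40. This reading sits badly with the Approach paragraph, which describes the 56 as already having FSST above 10 seconds, although the FSST is also listed under baseline testing, after screening. Even if accepted, it leaves about 40 randomised with no allowance for attrition. What stands is that only the sponsor can say which number is which.

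**Attrition may be lower than 25–30%.** The falls calculation uses 20%, which would leave 40 × 0.80 = 32, or 16 per group, still short of 20. The preliminary study kept 16 of 17, but over 16 weeks in a single group, and the plan itself quotes 25–30% beside the enrolment of 40.

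**It is a pilot.** That softens the consequence: the loss is mainly of precision. The plan nevertheless makes a detectable-difference claim for the FSST and tests at 0.05, and the lack of power it concedes concerns only the falls aim.

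**The power figures rest on an unstated 80%.** This is correct, and they should be read as conditional. The evaluable numbers do not need that assumption, and the rise from 25% to 29–30% hardly changes with it.

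**Conclusion.** The point holds, and the text is wrong as written. The two enrolment targets contradict each other. The sample-size section treats 40 enrolled as though it were 40 evaluable while quoting attrition that rules this out. On the plan's own figures and equal allocation, the primary comparison would fall 5–6 per group short of the 20 it relies on. Taking that 20 as given, the FSST claim does not hold for 40 enrolled; whether 20 is itself adequate cannot be checked from the document. The fit of 56 with the attrition range makes it the likely intended target. The class-size check supports this but is not needed for the conclusion.

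**What to change.** State one enrolment target in both sections and show the attrition step.

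- **If 56 is the target:** change the sample-size section to say that 56 will be enrolled so that, after 25–30% attrition, about 40 (20 per group) are evaluable. At the 30% end this gives 19.6 per group; full cover of the range would need 58.
- **If 40 is the target:** change Methods to 40, give the evaluable number as 14–15 per group, and restate the detectable difference at about 29–30%, with the power, SD and base that it assumes.
- **If either number counts people consented rather than randomised:** say so, and apply attrition to the number randomised.

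The first option costs wording only, since Methods already commits to 56. The second makes the stated detectable difference less favourable. The third may change the evaluable number, depending on what the sponsor meant.

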The MMBI will be held 3-times a week for an hour and will consist of a group dynamic balance class (30 minutes), a supervised obstacle course (10 minutes), and lower extremity and core strengthening (20 minutes). The group exercise class will focus on dynamic weight shifts with an emphasis on the lateral and diagonal directions. Over the 24 weeks of class the exercises will gradually increase in difficulty to challenge balance. A skilled instructor will lead each class and 1-2 assistants will be present to assist with fall risk prevention. The supervised obstacle course will focus on obstacle negotiation, gait over challenging surfaces, and moving in lateral, diagonal, and backward directions. Strength training of the lower extremities and core will focus on strengthening the major muscles of the lower extremity and core (hip flexor/extensors, hip abductors/adductors, knee flexor/extensors, ankle plantar flexor/dorsiflexors, ankle invertors/evertors, and core abdominal/back extensor muscles) utilizing commonly available gym equipment, ankle weights and body weight. Because our group program will utilize commonly available equipment for both the balance training and the strengthening portion our MMBI can be easily implemented in a community environment.

After completion of the intervention, subjects will repeat the baseline assessments. The testers will be blinded to group assignment. All participants will be encouraged to continue performing their exercises at home (home maintenance). They will be followed for an additional

6 months after completion of testing utilizing post-cards and monthly phone calls from the coordinator to determine the number of falls, near falls, injuries and fall related medical visits.

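### Aim 1 promises intention-to-treat, but the change-score ANOVA drops anyone without a 24-week test, and nothing provides for testing people who stop attending

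*Combined protocol and SAP*

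**What the plan says.** The Statistical Analysis paragraph sets the general rule: "All analyses will be conducted using the intention-to-treat principle".

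The Aim 1 paragraph that follows is to "compare changes (defined as 24-week value minus baseline value) in mobility, balance and strength between our two groups", and for this "we will use ANOVA for all continuous outcome measures (change=group"). Group is the only term. The co-primary endpoints fit this model: "The primary outcome measures will be the change from baseline to 24 weeks in the FSST and the FGA".

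Methods/Study Procedures gives two assessment points: "Assessments will occur at baseline and after completion of the intervention". After describing the two classes, it adds: "After completion of the intervention, subjects will repeat the baseline assessments". 

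The sample size section states "Typical attrition rates are 25 to 30" per cent, attributed mainly to competing commitments and unrelated illness. The Aim 2 calculation in the same section uses 20%. In Preliminary Studies, 1 of 17 participants did not finish.

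The documents define no analysis set, name no method for missing 24-week values, plan no sensitivity analysis, and do not say whether people who leave the classes are to be retested.

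**The concern.** A change score needs both measurements. Under the stated model, a randomised participant with no 24-week value contributes nothing to the comparison, so the analysed population is those who were retested, not those who were randomised. The plan itself expects a substantial loss and has one post-baseline visit, with no intermediate value to draw on.

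Two statements in the protocol make it unsafe to assume that the loss is harmless. The second Aim 1 hypothesis predicts better adherence to MMBI than to Tai Chi. Adherence is not the same as lacking a 24-week test, but the two are likely to be related, so loss may differ by arm. Preliminary Studies also reports that participants with slow baseline FSST improved most, so uneven loss of slow or fast steppers would shift the mean change in one arm relative to the other.

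The sample size section says the pilot's purpose is to estimate effect sizes for a confirmatory trial. An estimate from a selected subset, presented as intention-to-treat, weakens that main product.

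**Working it through.** **1. Rule against method.**
- Rule: all analyses by intention-to-treat.
- Method: change = group, where change is the 24-week value minus the baseline value.
- Data: one post-baseline test. The follow-up of all participants by telephone and postcard records falls and their consequences. It serves Aim 2 and cannot supply FSST, FGA, gait, strength or walk values.
- Result: rule and method agree only if everyone randomised is retested or missing values are imputed. The plan specifies neither.

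**2. The plan's own figure.** The sample size section says 20 per group detects a 25% difference in FSST. It gives no SD and no power, so the figure cannot be reproduced. Differences are therefore expressed below in SD units.

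**3. Numbers analysed.** Enrolment is 40 in the sample size section and 56 in Methods. Retested = N × (1 − attrition).

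| Enrolled | 25% attrition | 30% attrition | Left out |
|---|---|---|---|
| 40 | 30 (15 per arm) | 28 (14 per arm) | 10–12 |
| 56 | 42 (21 per arm) | 39.2, about 39 | 14–17 |

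Conversely, 40/0.75 is about 54 and 40/0.70 about 58, a range that contains 56. This suggests, without proving it, that 20 per group was meant as a count of completers.

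**4. Detectable difference.** Two-sample t test, two-sided alpha 0.05, 80% power, noncentral t, equal loss in both arms.

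| Per arm | Detectable difference (SD) |
|---|---|
| 20 | 0.91 |
| 15 | 1.06 |
| 14 | 1.10 |
| 21 | 0.89 |
| 20 and 19 | 0.92 |

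With 40 enrolled, the detectable difference grows by 1.06/0.91 to 1.10/0.91, about 17 to 21%. If 20 per arm was meant to give 80% power (an assumption), power falls to about 67% at 15 per arm and 64% at 14. With 56 enrolled, it stays at 0.89–0.92 SD, close to the 0.91 for 20 per arm.

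**5. Direction of bias.** This is an illustration, not an estimate. Assume retested participants gain 24% with MMBI (the FSST result in Preliminary Studies) and 12% with Tai Chi (the general balance figure in the Background), and leavers gain nothing. The difference among the retested is always 24 − 12 = 12 points. The difference among all randomised is (1 − dM) × 24 − (1 − dT) × 12, where dM and dT are the losses in the MMBI and Tai Chi arms.

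| Loss, MMBI / Tai Chi | All-randomised difference | Complete-case difference |
|---|---|---|
| 25% / 25% | 0.75 × 24 − 0.75 × 12 = 9.0 | 12 |
| 15% / 35% | 0.85 × 24 − 0.65 × 12 = 12.6 | 12 |
| 10% / 40% | 0.90 × 24 − 0.60 × 12 = 14.4 | 12 |

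Overall loss is 25% in every row, given equal arms. The complete-case result is too large in the first row and too small in the other two.

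**The case against.** The strongest reply is that nothing restricts testing to completers. The primary outcome is defined by time, at 24 weeks. The protocol elsewhere uses the end of the intervention as a time marker for everyone, as when all participants receive postcards. The falls follow-up of all participants is dated from post-intervention testing, which presupposes a test, and the timeline schedules post-testing by cohort and month. On this reading the plan is merely silent on missing data, and a change-score ANOVA could meet intention-to-treat if everyone were retested or values were imputed.

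This stands in part. A reader might infer that the plan bars leavers from testing, or that its method can never satisfy intention-to-treat. The documents support neither. They do, however, make no arrangement to retest leavers, and the ANOVA as stated still omits anyone untested.

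The size of the loss is also uncertain. The 25 to 30% is only called typical, Aim 2 uses 20%, and the preliminary study lost 1 of 17 (5.9%). The mismatch arises at any non-zero loss, but its importance grows with it. Enrolling 56 would largely offset the loss of power, but extra recruitment does not undo selection.

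Finally, the adherence hypothesis belongs to Aim 1 and needs no 24-week test, so the point is limited to the continuous outcomes.

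**Conclusion.** The point holds for the continuous Aim 1 outcomes, including both primary measures. As written, the plan promises intention-to-treat and specifies a complete-case analysis, in about 28–30 of 40 or 39–42 of 56 participants at the plan's typical attrition. The loss of precision (0.91 to 1.06–1.10 SD) applies only with 40 enrolled and equal loss by arm.

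A reader might infer that the completer effect must overstate the benefit and so undersize the next trial. The documents do not support this. Overstatement follows if, for example, loss is equal and leavers gain nothing, whereas the illustration reverses once Tai Chi loss is more than twice MMBI loss. The sample size section also says the next trial will be powered on falls, which are collected separately from the 24-week tests. The supportable conclusion is that the estimate may be biased in either direction, by an amount that the documents do not allow one to calculate.

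The plan should be changed. This is more than a request for detail, because a specific and inexpensive alternative would replace the stated method.

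**What to change.** - State that every randomised participant is invited to the week-24 tests whether or not they still attend classes.
- Replace change = group with an ANCOVA adjusting for the baseline value and the stratification factors (gender and FSST), with participants analysed in the arm to which they were randomised. Adjustment alone does not bring back untested participants, but it uses values already collected and weakens the assumption needed about the loss.
- Pre-specify one simple method for missing 24-week values, such as multiple imputation with few predictors. With 14 or 15 observed outcomes per arm, a rich imputation model would be fragile, and with one post-baseline visit a mixed model adds little unless it includes baseline or other predictors of dropout.
- Add a sensitivity analysis that sets non-returners to no change.
- Label any completer result as secondary, and report numbers and reasons for missing tests by arm.

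The cost is protocol and analysis wording, modest programming and some effort to bring back people who stopped. The estimate may be smaller than a completer estimate.
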